3.2 Inclusion Criteria

Age 18 or over

Histological confirmation of colorectal cancer or adenoma (group specific) or in group 8 symptoms raising suspicion of colorectal cancer (anaemia, rectal bleeding, alteration in bowel habit, weight loss, abdominal pain and over the age of 50)

Willingness to consent

Willing to return to enrolling medical site for all study assessments

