**TITLE OF THE PROTOCOL: RAMAN SPECTROSCOPY AND
COLORECTAL CANCER: TOWARDS EARLY DIAGNOSIS AND
PERSONALISED MEDICINE**

Short title/Acronym: Raman spectroscopy and colorectal cancer

Sponsor:

Representative of the Sponsor:

[name]
R&D Manager
R&D Department
Morriston Hospital
Swansea
[name]

REC reference: 14/WA/0028

STUDY SUMMARY/SYNOPSIS

TITLE	Raman spectroscopy and colorectal cancer: towards early diagnosis and personalised medicine
SHORT TITLE	Raman spectroscopy and colorectal cancer
Protocol Version Number and Date	ABM/RS/v4 Version 4;08/2/2017
Methodology	Prospective cohort observational study
Study Duration	5 years 6 months
Study Centre	ABM University LHB and Swansea University
Objectives	To explore the feasibility of detecting presence of differing stages of colorectal cancer at different phases of treatment using Raman spectroscopy
Number of Subjects/Patients	1,800 across 8 study groups
Main Inclusion Criteria	Stage T3/4 colorectal cancer (group 1) n=300 T1/2 early colorectal cancer (T1/2) from Bowel Screening Wales programme (group 2) n=300 Benign colorectal polyps (>1cm size)(group 3) n=200 Matched controls (without history of inflammatory bowel disease or familial bowel cancer)(group 4) n=300 Locally advanced rectal cancer requiring chemoradiotherapy (group 5) n=80 Bowel cancer patients at high risk of developing metastatic disease (group 6) n=20 Patients diagnosed with other cancer types (e.g. lung, pancreas)(group 7) n=300 Patients in primary care with colorectal symptoms (group 8) n=300
Statistical Methodology and Analysis	Principal Components Analysis (PCA) and hierarchical cluster analysis to measure accuracy, sensitivity and specificity measures for each patient group.

Protocol Agreement Page

The clinical study as detailed within this research protocol (**Version 2, dated 9th May 2014**), or any subsequent amendments will be conducted in accordance with the Research Governance Framework for Health & Social Care (2005), the World Medical Association Declaration of Helsinki (1996) and the current applicable regulatory requirements and any subsequent amendments of the appropriate regulations.

Chief Investigator Name: [name] [name] (Consultant Surgeon)

Chief Investigator Site: Singleton Hospital, Swansea

Contact details: [contact]
 Email: [contact]
 Fax:

Signature and Date:

Statistician Name: [name], Swansea Trials Unit

Contact details: Tel No:
 Email:[contact]
 Fax:

Signature and Date:

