3.1 Number of Subjects and Subject Selection

Paired plasma, faecal samples will be obtained from 300 patients with advanced colorectal cancer (stage T3/4) prior to surgical treatment (group 1). Plasma samples only will be obtained from 300 early colorectal cancers (T1/2) from the Bowel Screening Wales programme (group 2), 200 patients with benign colorectal polyps (>1cm size)(group 3) and 300 matched controls (without history of inflammatory bowel disease or familial bowel cancer)(group 4). The programme of work will be expanded to include 80 patients with locally advanced rectal cancer requiring chemoradiotherapy (group 5) who will have samples taken at diagnosis, during and after chemoradiotherapy and after resection of their tumour to identify changes in the spectra at each stage of treatment. Spectra can be compared with pathological factors, including tumour regression grade as a response to chemoradiotherapy, to establish if spectral analysis before CRT can predict the degree of downstaging seen. A further group of interest will be those at high risk of developing metastatic disease (group 6), for example colorectal cancers of advanced stage demonstrating adverse pathological features such as lymphovascular invasion or lymph node metastases. These twenty patients will have serial blood tests performed at five time-points over a 2 year follow up period, in parallel with standard investigations such as radiological imaging and tumour marker analysis. This aims to detect spectral change which predates development of liver or lung metastases on standard imaging modalities. This would have the potential of diagnosing metastatic disease at a pre-clinical stage affording earlier access to treatment. To establish if the spectral signatures are specific to colorectal cancer, a group of 300 patients diagnosed with stage-matched non-colorectal cancers (for example, lung cancer, pancreatic cancer, prostate cancer, endometrial cancer) will be studied with a single blood test for comparison.

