3.3 Exclusion Criteria

Under age 18

Patients with genetic conditions associated with colorectal cancer (Lynch syndrome and familial adenomatous polyposis)

Patients with inflammatory bowel disease

Unwilling/ unable to consent to trial participation

Patients from vulnerable groups

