4.2 Screening Procedures

Potential participants from groups 1,2,5 and 6 will be identified from colorectal cancer MDT meeting by their usual clinician who will be a named co-investigator. Patients in groups 3, 4 and 7 will be identified from attendance at routine surgical outpatient clinic or ward in-patient encounter by the co-investigators. Patients from group 8 will be identified by their usual GP at the time of first presentation.

Patients' records will be screened by the potential participant's existing clinical care team to establish if inclusion/exclusion criteria are met.

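### Section 3.2 gives groups 4 and 7 no route into the study, the control definition does not keep out sporadic colorectal neoplasia, and blood in groups 2 and 3 is not placed before lesion removal

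*Protocol*

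**What the plan says.** The synopsis plans "1,800 across 8 study groups" and lists all eight, including groups 4 and 7, in its row of main inclusion criteria.

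Section 3.2 then sets the eligibility conditions. Apart from age, consent and willingness to attend, the single disease-related condition is "Histological confirmation of colorectal cancer or adenoma (group specific) or in group 8 symptoms raising suspicion of colorectal cancer".

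Section 3.1 defines the two groups at issue as "300 matched controls (without history of inflammatory bowel disease or familial bowel cancer)(group 4" and "a group of 300 patients diagnosed with stage-matched non-colorectal cancers". Section 4.2 gives their source: "Patients in groups 3, 4 and 7 will be identified from attendance at routine surgical outpatient clinic or ward in-patient encounter". It also has the clinical team screen records to establish whether the inclusion and exclusion criteria are met.

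The exclusions in section 3.3 that concern bowel disease are inflammatory bowel disease and "Patients with genetic conditions associated with colorectal cancer (Lynch syndrome and familial adenomatous polyposis".

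On timing, section 3.1 takes samples from patients with "advanced colorectal cancer (stage T3/4) prior to surgical treatment (group 1" and gives group 5 named time points around chemoradiotherapy and resection. For group 2 (T1/2 cancers from the screening programme) and group 3 (benign polyps over 1 cm) it asks for blood without relating it to removal of the lesion. Section 4.4 allows groups 1 to 4 one month for one sample and for recording diagnosis and, where relevant, stage.

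**The concern.** Eligibility and sample timing belong in the protocol, so this is not detail that a separate analysis plan would be expected to supply.

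First, the team screening records under 4.2 must apply 3.2. Read literally, every control and every other-cancer patient fails it or enters as a deviation.

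Second, the primary objective in section 2.1 is an association between spectral signature and colorectal malignancy, and section 7.1 aims for sensitivity and specificity above 85%. Group 4 is a main source of non-cancer spectra for both. A control with a past colorectal cancer, a known polyp or an undiagnosed tumour satisfies everything written about that group, and would be labelled as free of disease.

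Third, histology is an entry condition in groups 2 and 3. Where the lesion is removed whole to obtain that histology, it has gone before the patient qualifies, and the one research sample is then taken without it. The protocol itself treats this as relevant: group 5 is sampled after resection in order to see how spectra change. If they do change, groups 2 and 3 may mix two states, and these are the groups on which any claim about early detection depends.

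**Working it through.** **Planned total.** Group sizes from the synopsis: 300 + 300 + 200 + 300 + 80 + 20 + 300 + 300 = 1,800. The plan's own figure is reproduced.

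**Route into the study under 3.2.**

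| Groups | Route | n |
|---|---|---|
| 1, 2, 3, 5, 6 | histology of colorectal cancer or adenoma | 300 + 300 + 200 + 80 + 20 = 900 |
| 8 | symptoms | 300 |
| 4, 7 | none | 300 + 300 = 600 |

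So 1,200 have a route and 600 do not; 600/1,800 = 33.3%. The qualifier about groups in the criterion divides cancer from adenoma among the groups. Only group 8 is given an alternative to histology.

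**What is required of a control.** Taking sections 3.1, 3.2, 3.3 and 4.2 together: adult, consenting, matched (on what is not said), no inflammatory bowel disease, no familial bowel cancer or the two named syndromes, and attending a surgical clinic or ward. None of these removes known or past sporadic colorectal neoplasia, and no bowel examination is asked for. Section 4.4 has a diagnosis recorded but names no reference test. For group 8, by contrast, section 3.1 compares the test with a final diagnosis.

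**Timing.** Group 1 is sampled before surgery and group 5 has four named points. Groups 2 and 3 (300 + 200 = 500) have one sample and no stated order relative to removal.

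**Illustration only.** Neither share below is in the documents. Assume true sensitivity and specificity of 85%, the level in section 7.1, and a fixed classifier.

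*Controls.* Let q be the share of group 4 with unrecognised disease, detected with the same sensitivity. Observed specificity = 0.85(1 − q) + 0.15q = 0.85 − 0.70q.

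| q (assumed) | observed specificity |
|---|---|
| 1% | 84.3% |
| 2% | 83.6% |
| 5% | 81.5% |
| 10% | 78.0% |

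*Group 2.* Let r be the share sampled after removal. In the worst case their spectra have fully reverted, so they test positive at the control rate of 15%. Observed sensitivity = 0.85(1 − r) + 0.15r = 0.85 − 0.70r.

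| r (assumed) | observed sensitivity, worst case |
|---|---|
| 10% | 78.0% |
| 20% | 71.0% |
| 25% | 67.5% |
| 50% | 50.0% |

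With partial or no reversion the loss is smaller or nil. The second table does not apply to group 3, whose polyps are benign and do not enter cancer sensitivity. There the effect would fall on the separation of polyps from controls.

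**The case against.** The strongest reply is that the study as a whole plainly intends to enrol both groups. The synopsis lists them as inclusion criteria, 3.1 defines them and 4.2 says where they come from. That stands. A reader might infer from 3.2 that a third of the study is excluded, but the documents do not support it; what they show is a contradiction between sections.

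On timing, the protocol nowhere says that blood is drawn after removal. Histology may come from biopsy, as it must for group 1, which falls under the same criterion and is sampled before surgery. Stage and diagnosis may also be completed during the month of participation. This stands too: sampling before removal is possible. It is not required, however, and the contrast with group 1 makes the omission visible. The study scheme diagram (section 2.3) and the participant information sheets are not in the text at hand. If they fix the timing, section 3.1 should say the same.

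A reader might also infer that blood taken after removal cannot carry the signature. The protocol leaves that open: section 1.1 envisages plasma markers that persist after resection, and group 5 is there to study the change.

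Nor does specificity rest on group 4 alone. Group 7 addresses whether the signature is specific to colorectal cancer, and group 8 supplies patients whose final diagnosis is benign. The control effect is also modest at low q (0.7 percentage points at 1%) and, in that simple model, understates specificity. Finally, this is an exploratory observational study whose results are withheld from group 8 patients and their GPs, which limits immediate harm.

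**Conclusion.** The point holds in three parts of unequal weight. Section 3.2 contradicts the synopsis, 3.1 and 4.2 for 600 of 1,800 participants (33.3%); this is certain on the text, but it is a drafting contradiction and not a measure of bias. The control definition leaves out current, past and unrecognised sporadic colorectal neoplasia in a group of 300; this is also clear from the text. For 500 patients in groups 2 and 3 the text permits sampling after lesion removal by not ruling it out; whether it happens, and how often, is not known.

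The bias cannot be sized from the documents. The figures for q and r only show direction and scale under stated assumptions, and the r figures are a worst case that assumes full reversion to control. They should not be quoted as expected losses. The matter should be fixed, but given the exploratory purpose it does not by itself invalidate the study.

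**What to change.** Amend section 3.2 so that each group has its own criteria, consistent with 3.1 and the synopsis:

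- **Group 4:** exclude known current or past colorectal neoplasia. Where a bowel examination has already been done in routine care, use it to confirm status. Flag controls without one and test their influence in a sensitivity analysis.
- **Group 7:** require a confirmed non-colorectal cancer and no known colorectal cancer.
- **Groups 2 and 3:** take the research sample with the lesion in place, as for group 1. Record the date of removal alongside the collection date, which section 5.3 already puts on each sample. Leave samples taken after complete removal out of the primary comparison.

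The cost is a protocol amendment and one additional date per patient in groups 2 and 3; no new procedure is needed. Some controls and some group 2 and 3 samples will be lost to the primary analysis. Examined controls may also be a more selected group than those met in practice, which is why unexamined controls are better flagged and kept for a sensitivity analysis than refused.

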3.3 Exclusion Criteria

Under age 18

Patients with genetic conditions associated with colorectal cancer (Lynch syndrome and familial adenomatous polyposis)

Patients with inflammatory bowel disease

Unwilling/ unable to consent to trial participation

Patients from vulnerable groups

3.4 Criteria for Premature Withdrawal

If the participant withdraws consent for the study then their samples will be removed from the analysis according to the patient's wishes.

4. Study Procedures

4.1 Informed Consent Procedures

Written informed consent will be obtained by named doctors of the research team after sufficient time is allowed to read and understand the study with assistance from the written patient information sheet. A specific consent form is included for the group 8 primary care patient group. Please refer to appendices 2-6 to see the separate patient information booklets.

Sufficient time will be allowed for the potential participant to decide to take part in the study. It is recognised that in most circumstances patients may prefer to provide the blood sample at the same time as the screening and consent visit, particularly if routine care blood tests are required at the same time. Investigators must ensure that the potential participant does have sufficient time to consider study inclusion however. A copy of the consent form will be kept in the patient's case notes. Patient's ongoing willingness to participate in the study will be recorded each time an additional blood test is taken (groups 5 and 6 only).

4.2 Screening Procedures

Potential participants from groups 1,2,5 and 6 will be identified from colorectal cancer MDT meeting by their usual clinician who will be a named co-investigator. Patients in groups 3, 4 and 7 will be identified from attendance at routine surgical outpatient clinic or ward in-patient encounter by the co-investigators. Patients from group 8 will be identified by their usual GP at the time of first presentation.

Patients' records will be screened by the potential participant's existing clinical care team to establish if inclusion/exclusion criteria are met.

4.3 Schedule of assessment for each visit

Blood sampling- a 5mL blood sample will be obtained from the participant. Serum will be obtained by centrifugation at 3,000 rpm for 10 min and stored at 4°C until analysed. Alternatively the serum may be stored at -80 degrees C until analysis.

Faecal samples will be collected by participants onto the spatula within in a 5mL faecal collection universal container. Samples will be stored at 4°C and will be analysed within 3 days to prevent degradation. Samples will be serially diluted prior to analysis to optimize wavelength detection.

Samples will be subject to Raman analysis with the aim of optimising excitation wavelength and spectral reproducibility. The Raman system (InVia Renishaw) is capable of both 785 nm and 532 nm studies. Comparisons across different patient groups will help determine the best wavelength conditions for reliable data acquisition, sample handling and data reproducibility. Unlike previous published studies, laser power degradation effects on the sample will be tested, as reproducibility is key in identifying the origins of spectral differences from the patient groups. To overcome the inefficiency of Raman scattering it is proposed that through using multiplexed surface-enhanced Raman scattering (SERS) gold nanoparticles functionalised to specific surface markers a unique spectral pattern will be identified. We will analyse blood, faeces and the reference biopsy sample with combinations of functionalised Ag-nanoparticles (labelled with EpCAM, CD44, MUC-1, CK20, CEA) and analyse the resultant spectral peaks and be compared to positive controls. These tests will give unique insight into the potential diagnostic ability of Raman spectroscopy for colorectal cancer.

To optimise the nanoparticle functionalisation and SERS detection an initial programme of work will study the blood, tissue and faecal samples from patients with advanced disease and establish the optimal antibody pairing from a potential panel of five antibodies associated with colorectal cancer cells.

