5.5 Sample storage procedures

All samples will either be analysed within 3 days of collection to minimize the chance of degradation, or stored at -80 degrees C until analysis. After analysis, all samples will be destroyed in accordance with the Human Tissue Act.

6. Safety measures

The safety of trial subjects will precedence over any other aspect of the trial. Consequently, prior to the initiation of laboratory work, lines of communication will be established with the study sponsor, to ensure that any issues that may impact on patient safety are reported without delay. These may include, but are not limited to, the reporting of unexpected or out of range results and significant deviations from the clinical protocol or work instructions.

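### The protocol contradicts itself on blood fraction and nanoparticle metal, and allows two storage routes with no rule balancing them across groups, so handling can become confounded with diagnosis

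*Protocol*

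**What the plan says.** **Blood fraction.** Protocol section 3.1 names plasma for the advanced cancers ("Paired plasma, faecal samples will be obtained from 300 patients with advanced colorectal cancer (stage T3/4) prior to surgical treatment (group 1") and for the early cancers ("Plasma samples only will be obtained from 300 early colorectal cancers (T1/2) from the Bowel Screening Wales programme (group 2"). The second sentence carries on to the polyp group and the controls. Section 4.3, which makes no distinction by group, instead says "Serum will be obtained by centrifugation at 3,000 rpm for 10 min and stored at 4°C until analysed".

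**Particle metal.** Section 4.3 proposes "surface-enhanced Raman scattering (SERS) gold nanoparticles functionalised to specific surface markers". Its next sentence says that the samples will be analysed with "combinations of functionalised Ag-nanoparticles".

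**Storage.** After the 4°C sentence, section 4.3 adds: "Alternatively the serum may be stored at -80 degrees C until analysis". Section 5.5 requires all samples to be either "analysed within 3 days of collection to minimize the chance of degradation, or stored at -80 degrees C until analysis". Neither section says when, or for whom, each route is used.

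**Context.**
- Section 4.2 identifies groups 1, 2, 5 and 6 at the cancer MDT meeting, groups 3, 4 and 7 in surgical outpatients or on the ward, and group 8 through the GP.
- Section 4.3 begins optimisation on samples from advanced disease, and expects comparisons between patient groups to help settle the wavelength and the sample handling.
- Section 5.5 has samples destroyed once analysed.

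**The concern.** The primary objective in section 2.1 is an association between the Raman signature and colorectal malignancy. The primary endpoint in the same section is the detection of nanoparticles. The specimen and the reagent are therefore what is being measured, and the protocol defines each of them in two incompatible ways.

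The storage option raises a different problem. The analysis in section 7.2 is built on principal components, which follow the largest sources of variation in the spectra whatever their cause. If storage or run date leaves a mark on the spectrum and is distributed differently across the diagnostic groups, that mark appears as a group difference. Where handling and group coincide completely, no analysis can separate them, and because samples are destroyed they cannot be measured again. The protocol itself treats degradation as a real possibility, since that is the reason section 5.5 gives for its 3-day limit.

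**Working it through.** **Step 1. Compare the statements.**

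| Item | One statement | Other statement | Reading |
|---|---|---|---|
| Blood fraction | plasma, groups 1 to 4 (3.1) | serum, no group distinction (4.3) | contradiction |
| Particle metal | gold (4.3) | Ag, next sentence (4.3) | contradiction |
| Storage | 4°C with no limit in that sentence, or -80°C (4.3) | analysed within 3 days, or -80°C (5.5) | permitted choice; no allocation rule; 4°C wording needs the 3-day limit |

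**Step 2. Is any of this tied to a group?** Not explicitly. Plasma is named for cancers, polyps and controls alike. The serum and particle sentences apply to everyone. Section 5.1 sends all blood on ice, and section 5.2 uses one laboratory. Three features can nevertheless create a link: recruitment source follows diagnosis (4.2), early laboratory work is weighted to advanced cancer (4.3), and handling is to be informed by comparing the groups (4.3). The synopsis gives a study duration of 5 years 6 months, which leaves room for handling to drift.

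**Step 3. How large could the effect be?** The protocol gives no figure for the effect of handling on spectra, so the following is an illustration for a single spectral score, not a model of the whole PCA and cluster analysis.

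Inputs:
- 300 against 300, from sections 3.1 and 7.1.
- Assumed: no cancer effect, within-route SD of 1, and a two-sided test at 0.05.
- Assumed, shown as ranges: a shift of *h* SD between storage routes, and a between-group difference Δ in the share stored at -80°C, centred on 50%.

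Formulas:
- p_A = 0.5 + Δ/2 and p_B = 0.5 − Δ/2
- variance in each group V = 1 + h²p(1 − p)
- SE = √(V_A/300 + V_B/300)
- d = hΔ/SE
- rejection rate = Φ(d − 1.96) + Φ(−d − 1.96)

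Worked case, h = 0.5 and Δ = 0.25: the shares are 0.625 and 0.375, so p(1 − p) = 0.2344 in both groups. V = 1 + 0.25 × 0.2344 = 1.0586. SE = √(2 × 1.0586/300) = 0.0840. d = 0.125/0.0840 = 1.488. The rejection rate is Φ(−0.472) + Φ(−3.448), about 0.319.

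False-positive rate:

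| h (SD) | Δ = 0 | 10 points | 25 points | 50 points |
|---|---|---|---|---|
| 0.25 | 5% | 6% | 12% | 33% |
| 0.5 | 5% | 9% | 32% | 85% |
| 1 | 5% | 20% | 79% | about 100% |
| 2 | 5% | 41% | 99% | about 100% |

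**Step 4. What of apparent accuracy?** At a 25-point imbalance the spurious AUC is only 0.52, 0.53, 0.57 and 0.61 for h = 0.25, 0.5, 1 and 2. With complete separation of storage by group, AUC = Φ(h/√2), which gives 0.57, 0.64, 0.76 and 0.92. Reaching 85% sensitivity and 85% specificity (the level in section 7.1) from handling alone then needs h = 2 × 1.036 = 2.07 SD. A test of association is therefore distorted by modest imbalance. A false 85% accuracy in such a score needs a large shift together with near-complete alignment.

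**The case against.** The strongest case against is that the protocol describes uniform handling. The fluid and metal conflicts are not linked to any group. A naming error that applies to everyone leaves the assay poorly specified but does not bias a comparison. Section 4.2 says where patients are found, not how their samples are treated. Sections 5.3 and 5.4 already give each sample a study number and collection date and track it through storage to analysis. Run order and batch composition may sit in a laboratory manual or an SAP that is not at hand.

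Much of this stands. It rules out three stronger readings that a reader might infer:

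- *That 4°C and -80°C contradict each other.* They do not. Section 4.3 offers -80°C as an explicit alternative, and section 5.5 gives compatible options. What is missing is an allocation rule.
- *That the fluid and metal conflicts themselves produce false group differences.* They would do so only if their use differed by group, and nothing in the protocol says it does.
- *That a classifier reading only storage would show some definite accuracy.* Suppose 80% of cancers and 20% of controls are frozen and storage is fully visible in the spectrum: 80% sensitivity and 80% specificity then follow, but this only returns the assumed inputs. A figure of 100% for both would need fluid to coincide with group, which runs against section 3.1.

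What the objection does not answer is that two laboratory instructions cannot both be followed, and that a free choice of storage remains open while handling is to be settled by comparing the very groups under study. Tracking records an imbalance; it does not prevent one.

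**Conclusion.** The point holds as a pair of contradictions plus an uncontrolled choice. The contradictions on blood fraction and particle metal are certain from the text and leave the measurement undefined. The confounding of storage and run date with diagnosis is a risk that the design permits, not something the protocol states will happen.

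Its size depends on two quantities the protocol does not give: the handling shift and the imbalance between groups. Under the assumptions shown, a 25-point imbalance takes the false-positive rate from 5% to between 12% and 79% for shifts of 0.25 to 1 SD. If storage is balanced the rate stays at 5% for every shift examined. Balance is within the sponsor's control even though the shift is unknown. Because samples are destroyed after analysis, prevention is worth far more than later adjustment.

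**What to change.** 1. Reconcile sections 3.1 and 4.3 to one blood fraction and one particle specification for all groups.
2. Align the open-ended 4°C wording in section 4.3 with the 3-day limit in section 5.5.
3. For the accuracy analysis, use one of the two permitted storage routes for every group, or balance the routes across groups.
4. Run samples in batches that mix the groups available at the time, in random order, with the operator seeing only the study number.
5. Record storage route, days stored and run date for each sample.
6. For samples already measured, check group comparisons within storage route wherever both groups are present. Where route and group coincide, no such check is possible, and that should be stated.

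**Cost.** Items 1, 2 and 5 are wording and record keeping. Batching delays results somewhat. If -80°C is chosen, every sample has a freeze-thaw and freezer space must be confirmed: the full design yields 1,700 + 80 × 4 + 20 × 5 = 2,120 blood samples, although the accuracy analysis needs fewer, and the capacity statement in section 5.4 is framed around equipment malfunction. If the 3-day route is chosen, mixing groups within a batch is harder, because it depends on who was recruited that week.

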5.1 Laboratory assessments

Raman analysis- 5mL blood will be required for each Raman analysis. Groups 1,2,3 and 4 will only require one blood sample (5mL total volume). Group 5 will have blood sampling on 4 occasions of 5mL per sample *ie* 20mL total. Group 6 will have 5mL of blood taken on 5 separate occasions *ie* 25mL blood in total.

Blood samples will be transferred to the Centre for NanoHealth laboratory in ILS-2 on ice to maintain the sample at 4 degrees centigrade. Faecal samples will be transported at room temperature.

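### Protocol section 4.3 looks to comparisons across patient groups to help settle wavelength, handling and reproducibility; such comparisons cannot estimate reproducibility, and no repeat measurement of the same sample is stated

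*Protocol*

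**What the plan says.** Section 4.3 makes technical optimisation an aim of measuring the study samples: "Samples will be subject to Raman analysis with the aim of optimising excitation wavelength and spectral reproducibility". Two excitation wavelengths are available: "The Raman system (InVia Renishaw) is capable of both 785 nm and 532 nm studies". The choice between them is to be informed as follows: "Comparisons across different patient groups will help determine the best wavelength conditions for reliable data acquisition, sample handling and data reproducibility".

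The same section states why this matters: "laser power degradation effects on the sample will be tested, as reproducibility is key in identifying the origins of spectral differences from the patient groups". It adds several probe combinations: "We will analyse blood, faeces and the reference biopsy sample with combinations of functionalised Ag-nanoparticles". It also describes a preliminary phase in which "an initial programme of work will study the blood, tissue and faecal samples from patients with advanced disease", to settle the nanoparticle functionalisation and the antibody pairing.

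On blood volume, section 5.1 says: "5mL blood will be required for each Raman analysis. Groups 1,2,3 and 4 will only require one blood sample (5mL total volume". It gives group 5 four samples of 5 mL (20 mL) and group 6 five samples of 5 mL (25 mL).

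Section 7.1 relies on an independent validation set of 300 per subgroup. Nothing in the protocol separates the samples used for technical tuning from that set.

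**The concern.** The protocol makes its reading of spectral differences depend on reproducibility, then names a comparison that carries no information on it. Patients in different groups differ in disease, in other biology and in measurement error, and a contrast between them shows only the sum.

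Three things are at stake.

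- **Choice of setting.** A wavelength or handling condition judged by group comparison can be preferred because it separates the groups in the samples at hand, partly by chance, and not because it measures reliably.
- **Validation.** If the samples used for that choice also enter the validation set, the reported sensitivity and specificity are no longer independent of the tuning.
- **Serial change.** Section 3.1 looks for spectral change during chemoradiotherapy (group 5) and before metastases show on imaging (group 6). Without the within-sample variation, there is no measure of how large a change must be to exceed measurement error.

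Section 5.5 has all samples destroyed after analysis, so replicates that were not planned cannot be recovered later.

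**Working it through.** **1. What each comparison can estimate.** Write one measurement as group mean + patient deviation (variance σ_b²) + measurement error (variance σ_w²).

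- The difference between two group means estimates the disease difference plus any error offset linked to group. It contains no estimate of σ_w.
- The spread within a group, with one measurement per patient, estimates σ_b² + σ_w². The two parts cannot be told apart.
- Only m ≥ 2 measurements of the same sample estimate σ_w², and with it ICC = σ_b² / (σ_b² + σ_w²).

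The serial samples in groups 5 and 6 do not fill the gap. Section 4.4 places those of group 5 at diagnosis, during and after chemoradiotherapy and after surgery, and spreads those of group 6 over two years. They record different states of the patient.

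**2. The volume figures.** Section 5.1 is consistent as volume per sampling occasion: 1 × 5 = 5 mL (groups 1 to 4), 4 × 5 = 20 mL (group 5), 5 × 5 = 25 mL (group 6). The statement that each Raman analysis needs 5 mL sits badly with section 4.3, which draws 5 mL, spins it to serum, and names two wavelengths, a laser test and several nanoparticle combinations.

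**3. Cost of purely random error.** Assumptions, none from the protocol: true difference d = 0.25 between-patient SD, n = 300 per group, two-sided 5% test, one measurement per patient.

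Power = Φ( d / (SD × √(2/n)) − 1.96 ), with SD = 1/√ICC and √(2/300) = 0.0816.

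- ICC 0.9: SD 1.054; 0.25/0.0861 = 2.90; power 0.83.
- ICC 0.7: SD 1.195; 0.25/0.0976 = 2.56; power 0.73.
- ICC 0.5: SD 1.414; 0.25/0.1155 = 2.17; power 0.58.

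With no measurement error, power would be 0.865. A simulation with no true difference and error SD equal to patient SD (4,000 runs, 300 v 300) rejected in 5.0%, so random error alone creates no false disease signal.

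**4. Error linked to group.** Same setting, error SD equal to patient SD, so the total SD is √2 and the standard error is 1.414 × 0.0816 = 0.1155.

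- Offset 0.3 patient SD: 0.3/0.1155 = 2.60; Φ(0.64) = 0.74.
- Offset 0.5 patient SD: 0.5/0.1155 = 4.33; Φ(2.37) = 0.99.

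The simulation agreed, with 74% and 99% false rejection. The offsets are assumed. Section 4.2 does recruit groups by different routes (MDT meeting, clinic or ward, GP), and sections 4.3 and 5.5 allow either short refrigerated storage or −80°C. The protocol does not say that storage differs by group.

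**5. Choosing between two wavelengths by group contrast.** With no true difference, the chance that at least one of two contrasts reaches 5% lies between 5% (the two fully correlated) and 1 − 0.95² = 9.75% (independent). For a single contrast the effect is modest. It matters if the same samples then serve as validation.

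**6. Yardstick for serial change.** The difference of two single measurements has error SD √2 × s_w, so a change within 1.96 × √2 × s_w = 2.77 s_w is compatible with measurement error alone. Without s_w this limit has no value.

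**The case against.** The strongest case against rests on four points.

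- **The wording is soft.** Group comparisons are said only to help determine the conditions. Section 4.3 also plans a laser-degradation test, positive controls and preliminary work within advanced disease. This stands: the protocol does not make group comparison the sole criterion. But a degradation test addresses damage from laser power, not agreement under fixed conditions, and none of these steps states a replicate or a repeatability criterion.
- **The volume does not rule out repeats.** A reader might infer from section 5.1 that 5 mL per analysis and 5 mL in total (5/5 = 1) make a second measurement impossible. The documents do not support that. Section 4.3 measures serum obtained from the draw, section 5.1 itself uses 5 mL as the volume per occasion in groups 5 and 6, and the work planned in 4.3 presupposes several measurements per sample. What remains is a phrase to reconcile.
- **Error is not the same as disease.** A reader might infer that, without replicates, measurement error cannot be told from disease differences. That goes too far. Random error merges with patient variation and costs power; only group-linked error would mimic disease, and the protocol shows no such link, only routes by which one could arise.
- **Replicate numbers belong elsewhere.** Aliquot counts and thresholds commonly sit in a laboratory procedure or the SAP, which is not shown, and this is an exploratory study. Their absence is indeed no finding. The point is that the protocol does state a basis for the choice, and that basis is unsuitable.

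It is also fair to want a wavelength that discriminates well. That is a legitimate second criterion, on samples kept apart from the validation set.

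**Conclusion.** The point holds in a limited form. Section 4.3 relies in part on a comparison that cannot estimate the quantity which the same section treats as essential, no same-sample repeat is stated, and nothing keeps the tuning samples out of the validation set. Section 5.1 needs reconciling with 4.3 on what 5 mL refers to.

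The protocol gives no within-sample variation, so the size can only be illustrated. Under the assumptions above, a setting with ICC 0.9 instead of 0.5 is worth power of 0.83 instead of 0.58. A group-linked offset of 0.3 patient SD would give about 74% false rejection, but only if such an offset exists. The conclusion that group contrasts do not measure reproducibility depends on none of these figures. The change should be made: it is cheap, and section 5.5 leaves no chance to repeat measurements later.

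**What to change.** - **Section 4.3.** Replace the sentence on comparisons across groups. Choose wavelength, laser power and handling from replicate aliquots of the same serum samples in a small fixed subset (for example three aliquots at each of 785 and 532 nm, in patients from groups 1 and 4). Judge by within-sample repeatability: the ICC to compare wavelengths, since their intensity scales may differ, and the within-sample SD for the chosen setting.
- **Section 7.1.** State that this subset is kept out of the independent validation set.
- **Groups 5 and 6.** Use the within-sample SD from the subset as the yardstick for serial change. It is a lower limit, because day-to-day variation within a patient adds to it.
- **Section 5.1.** Reconcile with 4.3 by restating the volume as 5 mL per sampling occasion, divided into aliquots, with the aliquot volume used for one acquisition.

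The cost is protocol wording and some extra spectrometer time. No extra blood, visits or patients are needed, provided that 5 mL is the volume per occasion, as 4.3 and the figures for groups 5 and 6 indicate.
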